#### *Exclusion Criteria*

- History of cardiac procedure(s) in a cardiac catheterization laboratory
- History of seizures, migraine headaches or severe susceptibility to motion sickness
- Currently taking psychotropic drugs or on long-term psychotropic treatment
- Unable to read and speak English
- Visually impaired
- Unable to provide written consent

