**Visit 1 - Baseline.** All participants will be required to meet with study personnel at an offsite locale (Spectrum Health facility whenever possible) prior to the scheduled LHC to conduct the baseline visit. Once informed consent is obtained, study personnel will administer the State Trait Anxiety Inventory (STAI) assessment to all participants.

**Randomization.** Following the completion of the STAI assessment, participants will be randomized in a 1:1 fashion to undergo either VR combined with standard procedural education or to standard procedural education alone. Prior to enrollment of the first participant, Spectrum Health Office of Research Administration statisticians (who are not be study personnel) provided the randomization assignment schema to Cardiovascular Research staff (also not study personnel). Each assignment was placed in an envelope in the order designated by the statisticians' assignment schema. The envelopes were sealed and sequentially numbered from "1" to "200". The envelopes were stored in the research office in the high-density storage area.

Due to the COVID-19 Pandemic, study personnel are now working primarily from home.

In order to maintain the randomization schema as designed as well as reduce the need for staff to go into the hospital to collect randomization envelopes (thereby reducing their risk of exposure), the randomization process will be, for the remainder of the study, via REDCap database. The coordinator attending the enrollment visit will use REDCap to learn the randomization assignment for that participant while in the field, thus maintaining the blind.

For participants randomized to standard procedure education alone, the baseline visit will be complete. Participants will be thanked (and provided a gift card) and remaining study activities will be reviewed.

For participants randomized to VR intervention, the following will occur:

- A baseline wellness self-assessment will be administered (reporting on absence or presence and degree of severity of headache, nausea, dizziness, fatigue and vision abnormalities)
- The participant will be asked to confirm she or he is seated comfortably and study personnel will ensure the chair and participant are free of direct obstruction

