- The participant will be shown the individual components of the VR system (View-Master with smartphone inserted; external speaker for audio projection; monitor for study staff to observe what the participant is experiencing), be given instructions on how to use the device and encouraged to ask questions.
- Once the participant indicates she or he is ready, they'll be asked to begin the VR experience. Study personnel will stay in the room with the participant for the entire duration and will be viewing on the monitor what the participant is experiencing virtually. Study personnel will provide guidance and answer questions regarding the technology and its use but will not answer questions regarding the facilities, prep, procedure or recovery (this will be explained prior to starting the VR experience).
- When the participant indicates she or he is finished with the VR experience and has had a few minutes to orient, the wellness self-assessment will be administered again.
- Participants will be thanked for their participation (and provided a gift card) and remaining study activities will be reviewed.

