### ***Visit 2 – Procedure Day***

Study personnel will meet participants in their Prep/Recovery room prior to their procedure and the STAI assessment will be administered to all. A Retrospective Wellness questionnaire will be administered to the VR intervention group only in order to assess for any longer-term adverse effects (e.g., headache lasting several hours) of the VR experience. Postprocedure, a patient preparedness survey will be administered to all participants. All participants will again be thanked for their participation, all questions will be answered and their study participation will conclude.

All of the above activities except for standard procedural education will be research related. The average study participation time frame for all participants will be less than 1 month.

The data collected for this study entails the State-Trait Anxiety Inventory results, wellness self-assessments results, preparedness survey results and meta-data results.

e. Data Management

The data collected for this study will comprise of survey results (State-Trait Anxiety Assessment; VR related wellness assessments; and a preparedness assessment) as well as demographic and medical history data (for general reporting purposes). The data will be collected directly from participants using paper tools, where after the responses will be entered into an electronic data capture (EDC) system. The study EDC will be housed on secure Spectrum Health servers and the paper documents will be stored in secure Spectrum Health facilities.

f. Withdrawal of Subjects

Participants may change their minds at any time and choose to withdraw from this study; however, there are no circumstances under which participants would be withdrawn without their consent.

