### **Pre VR Experience Wellness Self-Assessment**

Please identify if you are currently experiencing any of the following and rate the degree of severity of the symptom(s) on a scale from 1 (mild) – 5 (severe):

1. Headache:

No       Yes

1                    2                    3                    4                    5

2. Altered/Blurred/Double Vision:

No       Yes

1                    2                    3                    4                    5

3. Nausea:

No       Yes

1                    2                    3                    4                    5

4. Dizziness/Disorientation:

No       Yes

1                    2                    3                    4                    5

5. Fatigue:

No       Yes

1                    2                    3                    4                    5

Subject ID:

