### **Retrospective VR Experience Wellness Self-Assessment**

Please identify if you recall any of the following within 24 hours after your VR experience and rate the degree of severity of the symptom(s) on a scale from 1 (mild) – 5 (severe):

1. Headache:

No       Yes

1                    2                    3                    4                    5

2. Altered/Blurred/Double Vision:

No       Yes

1                    2                    3                    4                    5

3. Nausea:

No       Yes

1                    2                    3                    4                    5

4. Dizziness/Disorientation:

No       Yes

1                    2                    3                    4                    5

5. Fatigue:

No       Yes

1                    2                    3                    4                    5

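### Should the control arm also complete the retrospective wellness form, so that symptoms arising after the VR session have a comparator?

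*Combined protocol and SAP*

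**What the plan says.** Three wellness forms are used, all in the VR arm, and all cover the same five symptoms with a severity rating from 1 to 5 (Appendix C). The first is completed just before the VR session. After the session and a few minutes of reorientation, "the wellness self-assessment will be administered again" (Section 8d, Visit 1). Both of these ask about symptoms at that moment. The third is given on the procedure day: "A Retrospective Wellness questionnaire will be administered to the VR intervention group only in order to assess for any longer-term adverse effects", the example offered being a "headache lasting several hours". Its instruction reads "Please identify if you recall any of the following within 24 hours after your VR experience".

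Controls have no counterpart: "For participants randomized to standard procedure education alone, the baseline visit will be complete" (Section 8d, Randomization). At Visit 2 they complete only the anxiety inventory and the preparedness survey.

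Section 8c makes pre-procedure anxiety the primary outcome and preparedness a secondary analysis; wellness is not listed. Section 9b names tests for demographic variables and anxiety. It opens with general rules (counts for categorical variables, mean or median for continuous ones) that are not tied to particular variables. Section 8e lists the wellness assessments as data to be collected.

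**The concern.** The stated purpose of the retrospective form is to pick up effects of VR, which reads as a question of cause. Headache, fatigue, nausea, dizziness and visual disturbance can all occur without VR, so a VR-only count mixes background symptoms with any effect. A randomized control group attends the same Visit 2 and is not asked. The two Visit 1 forms show whether a symptom was present before VR or carried on from it. They say nothing about how often one would start in the following day anyway.

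At stake is the safety description. A raw count could make VR look harmful when it is not, or a real effect could be dismissed as background. With no analysis named for these forms, it may also seem that nobody has decided how to report them.

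**Working it through.** **1. The plan's own figure.** Section 9a gives 86 per group for an effect size of 0.5, 90% power and alpha 0.05. The two-sided two-sample t-test calculation gives 85.03, rounded up to 86, with power 90.3% at 86. The figure reproduces. It concerns anxiety, and nothing below alters it.

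**2. What the existing forms can show.** Cross-matching the three forms sorts each symptom in each VR participant:

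| Before VR | Just after VR | Recalled from next 24 h | Reading |
|---|---|---|---|
| Present | Either | Either | Already there before VR |
| Absent | Present | Present | Began around VR and persisted or recurred |
| Absent | Present | Absent | Began around VR; not recalled from the next 24 h |
| Absent | Absent | Present | Later onset; no background rate |

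A headache that starts with the session and lasts several hours, the protocol's own example, falls in the second row. Only the last row lacks a reference.

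**3. Size of that gap.** The documents give no symptom rates, so these are assumptions. If 10% to 30% of 86 already have a given symptom on a Visit 1 form, 86 × 0.90 = 77.4 down to 86 × 0.70 = 60.2 remain at risk. With a later-onset background of 5% to 20%, the reports expected with no VR effect run from 60.2 × 0.05 = 3.0 to 77.4 × 0.20 = 15.5. The exclusion "History of seizures, migraine headaches or severe susceptibility to motion sickness" (Section 8b) points to the lower end for headache and nausea, but does not bear on fatigue.

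As an invented example, 10 later reports among 70 is 14.3% (exact 95% interval 7.1% to 24.7%). That implies an excess of about 9 points if the background is 5%, and none if it is 14%. The raw rate can be described; the excess cannot.

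**4. What a control-arm form would add.** It would have to be reworded to refer to the 24 hours after the baseline visit. Controls have no Visit 1 wellness form, so the contrast would cover any symptom in that day, not later onset. The last row of the table would still have no comparator.

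Precision, using the Newcombe interval for a difference of proportions, which suits small counts. For equal observed proportions p with Wilson limits l and u, half-width = √[(p − l)² + (u − p)²].

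- 4/86 in each arm: p = 4.65%, Wilson 1.82% to 11.36%; √(2.83² + 6.71²) = 7.3 points.
- 26/86 in each arm: p = 30.2%, Wilson 21.5% to 40.6%; √(8.7² + 10.4²) = 13.5 points.
- 2/40 in each arm: p = 5.0%, Wilson 1.38% to 16.50%; √(3.62² + 11.50²) = 12.1 points.

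The simpler formula 1.96√[2p(1 − p)/n] gives 6.5 points at p = 5% with 86 per arm and 9.6 with 40 per arm, so it is optimistic at low rates.

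The figure of 40 per arm is an assumption. Section 8d shows that the study was already under way, since "the randomization process will be, for the remainder of the study, via REDCap database", and the number still to be enrolled is not given. At that size, 6/40 against 2/40 gives +10.0 points (−4.0 to 24.5), which cannot tell a 10-point excess from none.

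**5. Recall.** Participants know their arm. VR participants have seen the checklist twice before Visit 2; controls would be seeing it for the first time. If VR participants report 90% of true symptoms and controls 70% (assumed), then with no VR effect the apparent excess is (0.90 − 0.70) × p: 1 point at p = 5%, 3 points at 15%, 6 points at 30%. The confidence interval does not reflect this.

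**The case for a change.** The best case for acting is that the form is meant to detect effects of VR, that a randomized comparator is already in the building, and that the cost is about a minute (an estimate) per control at an existing visit. Given after the anxiety inventory, the form could not disturb the primary measurement. An imprecise contrast with its limits stated would, on this view, still tell more than no background rate at all.

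Much of this stands. The facts are right, the cost is low, and a VR-only count of later symptoms cannot support a causal statement.

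The inference about gain does not follow. The added form would answer a different question from the one that lacks an answer. It could not recover controls who have already finished. It would divide the VR arm between two wordings. Its likely bias runs towards VR harm, and at low symptom rates that bias comes on top of intervals wider than the effects of interest. Misreading is possible with or without it.

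The absence of a named analysis is a fair observation but a small one. The general rules in Section 9b cover yes/no items and ratings, and no test is needed for symptom monitoring outside the endpoints.

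**Conclusion.** No change to the plan follows. Giving the form to the exposed group only is a deliberate choice, stated with its reason, and it serves to monitor tolerability. The protocol promises neither a between-arm symptom comparison nor a causal safety conclusion.

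The limitation is real but narrow. It concerns symptoms absent on both Visit 1 forms and recalled later, perhaps 3 to 15 reports per symptom among 86 under the assumed rates, which cannot be attributed to VR. Analysts can handle this with data already collected, by cross-tabulating the three forms and presenting the result as description.

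Extending the form to controls is a debatable trade-off. It would give half-widths of about 7 to 14 points with 86 per arm, or about 12 points with 40 per arm at a 5% rate, and a possible spurious excess of 1 to 6 points. The symptom rates, the recall rates and the 40 per arm are assumptions, since the documents supply none of them. The conclusion depends more on two features of the design: wellness is not an endpoint, and a control form at Visit 2 would not isolate later onset. The primary comparison and its 86 per group are unaffected either way.

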### **c. Study Endpoints**

The primary measure of interest in the present study is patient anxiety, as measured using the State Trait Anxiety Inventory (2, 3).

In all patients, anxiety will be assessed using this tool at baseline (prior to randomization) and again on the day of the procedure, just prior to undergoing catheterization.

The primary outcome of this study is the anxiety level measured just prior to catheterization, which will be compared in the two study groups.

The preparedness tool results will be compared between the two groups as a secondary analysis.

d. Procedures Involved in the Research

**Standard procedural education.** Standard procedural education for all patients undergoing cardiac catheterization at our site formally comes from two sources. First, it is provided verbally by clinical personnel, including physicians and nurses, during routine clinical interactions (i.e. at the time of office visits) and during subsequent phone calls made by the patient to clinical personnel requesting additional procedural information. Second, clinical personnel provide all patients with an information sheet that describes cardiac catheterization (attached as Appendix A; also available online at [www.kramesondemand.com](http://www.kramesondemand.com)).

**Virtual reality.** The VR experience developed for this study will be provided to participants by study personnel using a smartphone (Moto G, Motorola, Schaumburg, Illinois) and a viewer headset (View-Master, Mattel, Segundo, California). This interactive VR experience was filmed using a commercially available camera (360fly 4K, 360FLY, Pittsburgh, Pennsylvania) and developed using proprietary software by Carnevale Interactive (Grand Rapids, Michigan). The VR simulation will allow participants to experience aspects of their procedural day, starting with arrival in the lobby of the catheterization center. The simulation will progress to the catheterization laboratory registration and waiting room, followed by the pre-procedural holding area and finally the procedure room. In each location, the participant will be able to virtually explore the space and have the option of clicking on certain objects of interest, which will trigger an audio description of the object and its purpose.

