### **Appendix C – Preparedness Survey**

Please circle your level of agreement with the following statements:

1. I know about the *reason for my planned procedure*.

Strongly Agree / Agree / Somewhat Agree / Somewhat Disagree / Disagree / Strongly Disagree

2. I understand the *purpose* of my planned procedure.

Strongly Agree / Agree / Somewhat Agree / Somewhat Disagree / Disagree / Strongly Disagree

3. I understand the *general activities* around my planned procedure.

Strongly Agree / Agree / Somewhat Agree / Somewhat Disagree / Disagree / Strongly Disagree

4. I felt prepared about how and where to park my car.

Strongly Agree / Agree / Somewhat Agree / Somewhat Disagree / Disagree / Strongly Disagree

5. I felt prepared about how and where to register for my procedure.

Strongly Agree / Agree / Somewhat Agree / Somewhat Disagree / Disagree / Strongly Disagree

6. I felt prepared about how to find my way to my destination.

Strongly Agree / Agree / Somewhat Agree / Somewhat Disagree / Disagree / Strongly Disagree

7. I felt prepared about what to expect in the Prep/Recovery room.

Strongly Agree / Agree / Somewhat Agree / Somewhat Disagree / Disagree / Strongly Disagree

8. I felt prepared about what to expect in the procedure room.

Strongly Agree / Agree / Somewhat Agree / Somewhat Disagree / Disagree / Strongly Disagree

9. Overall, I felt prepared for what to expect at the Meijer Heart Center for my left heart catheterization procedure.

Strongly Agree / Agree / Somewhat Agree / Somewhat Disagree / Disagree / Strongly Disagree

10. Due to my preprocedure education by Spectrum Health, I sought out further information.

Yes No If yes, please identify how ( e.g., used the internet, asked friends/family, called the office).

---

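### Does giving the preparedness survey after the procedure undermine items 1–3, which ask in the present tense what the patient knows?

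*Combined protocol and SAP*

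**What the plan says.** Section 8d, Visit 2, fixes the timing: "Postprocedure, a patient preparedness survey will be administered to all participants". Nothing elsewhere places the survey earlier. Section 8c makes the comparison of the survey between arms a secondary analysis. Section 9b names no method for it and defines no total score.

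On the form (Appendix C, Preparedness Survey), items 1–3 are in the present tense. Item 1 asks whether the patient knows the "reason for my planned procedure", item 2 whether the patient understands its purpose, and item 3 whether the patient understands the general activities "around my planned procedure". Items 4–9 look back; item 8, for example, reads "I felt prepared about what to expect in the procedure room". The only instruction on the form is to circle a level of agreement.

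Two other places bear on the point. Section 8b excludes patients with "History of cardiac procedure(s) in a cardiac catheterization laboratory". Section 8d describes what each arm receives. In the VR arm, "The VR simulation will allow participants to experience aspects of their procedural day, starting with arrival in the lobby of the catheterization center", and "In each location, the participant will be able to virtually explore the space and have the option of clicking on certain objects of interest". In both arms, "clinical personnel provide all patients with an information sheet that describes cardiac catheterization".

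**The concern.** One form, given at one time, uses two time frames. A patient who answers item 3 literally reports what is understood after the catheterization, not what the education had conveyed beforehand. Because earlier cardiac catheterization laboratory procedures are an exclusion, the day itself is each patient's first direct experience of what the VR previews. By the time of the survey the control arm has had that experience too.

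This would not favour either arm, since both are surveyed at the same point. It would tend to pull the arms together, so a real benefit of VR on understanding before the procedure could be missed. If all the agreement items were averaged, understanding after the procedure would also be mixed with remembered preparedness, in the one comparison that section 8c labels secondary.

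**Working it through.** **Which items can be affected**

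- *Items 1–2 (reason and purpose).* The VR shows places and objects. Reason and purpose come from the clinicians and the information sheet, which both arms receive. Little arm difference is expected whenever the items are asked, so there is little to lose.
- *Item 3 (general activities).* The VR could plausibly help here, and the day itself also teaches. This is the only item with a credible route to dilution.
- *Items 4–9.* These are already retrospective and suit a survey given afterwards. Items 5–8 cover registration, finding the way, the Prep/Recovery room and the procedure room, and item 9 covers overall preparedness. They largely match the VR sequence of lobby, registration and waiting area, holding area and procedure room.

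**How much could be lost on item 3**

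The documents give no figure, so this is an illustration that treats the six-category item as roughly continuous.

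The plan's own sample size comes first. An effect size of 0.5, two-sided α = 0.05 and 90% power in a two-sample t-test give 85.03 per group, rounded up to the stated 86 (power 0.903). That figure concerns anxiety and does not depend on the survey.

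The 95% half-width for a difference in means, in SD units, is t(0.975, n₁+n₂−2) × √(1/n₁ + 1/n₂). With 86 + 86 it is 0.301.

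Let d be the arm difference on item 3 before the procedure and f the fraction lost by asking afterwards. The expected difference is (1 − f)d, and the expected interval includes zero when f > 1 − 0.301/d:

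- d = 0.5 (borrowed from the anxiety endpoint): f > 1 − 0.602 = 0.398
- d = 0.4 (assumed): f > 1 − 0.753 = 0.247
- d = 0.3 (assumed): zero is included even with no loss

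So some 25% to 40% of a fairly large difference would have to vanish before this expected result changed. Nothing in the documents says whether f is near 0 or near 1.

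**What rewording mid-study would cost**

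The Randomization text speaks of procedures for the rest of the study, so enrolment appears to be under way. Assume that 75%, 50% or 25% of 172 remain, and compare arms only among those given the new wording. If the new wording recovered the whole of d, it would beat the unchanged form only when 1 − f < 0.301 / (new half-width).

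| Remaining | Split | Half-width (SD) | New wording better only if |
|---|---|---|---|
| 129 | 64 + 65 | 0.348 | f > 1 − 0.301/0.348 = 0.14 |
| 86 | 43 + 43 | 0.429 | f > 1 − 0.301/0.429 = 0.30 |
| 43 | 21 + 22 | 0.616 | f > 1 − 0.301/0.616 = 0.51 |

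At 43 remaining, even an undiluted d of 0.5 lies inside ±0.616. At 86 remaining, an undiluted d of 0.4 lies inside ±0.429.

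**What asking before the procedure would achieve**

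The existing contact before the procedure takes place in the patient's Prep/Recovery room. By then both arms have arrived and reached that room, so most of the previewed places have been seen in reality. Only the procedure room clearly remains. Much of the shared experience held against the later timing would already have happened.

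**The case for a change.** The best case for a change is that the facts are not in dispute and the change is cheap. The authors worded six items retrospectively and could have done the same for three more lines on a paper form. Some patients may answer items 1–3 as of beforehand and others as of now, and the reader cannot tell which. A null result on item 3 would then be ambiguous. Moving or rewording the items needs no new visit and leaves the sample size and primary analysis alone.

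The ambiguity stands, and it limits what a null result on item 3 can mean. The case for changing the form does not. The printing cost is small, but the cost in information is not: splitting one item into two versions gives up precision for certain, in exchange for removing a dilution that may not exist. A retrospective item 3 would still depend on recall and hindsight, as items 4–9 do. The literal reading is also uncertain, because the reference to a planned procedure, on a form otherwise about preparedness, may itself lead patients to answer about the time beforehand.

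The worry about mixing time frames assumes a pooled score that the plan never defines. Section 9b's silence on how the survey is analysed is a separate matter.

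**Conclusion.** The mismatch between tense and timing is real, but no change to the plan follows. It comes down to possible dilution of one item out of ten in a secondary survey, equal in timing for both arms, of unknown and possibly zero size, with most of that item's content covered by items 5–9. The primary outcome, its analysis and the 86 per group are untouched.

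Rewording now is a trade-off with no clear gain. Under the assumed 25% to 75% still to come, it pays only if the loss on item 3 exceeds about 51% to 14% respectively, and then only if the new wording removes the whole loss. Asking the items in the Prep/Recovery room would remove little of the shared exposure.

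What remains is reporting that an analyst would do sensibly without instruction: show items 1–3 apart from items 4–9, describe them as understanding stated after the procedure, and do not read a null result on item 3 as evidence that VR failed to improve understanding beforehand. With no pooled score in the plan, this alters no planned result.

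The half-widths rest on treating a six-category item as continuous. The values of d and the fractions remaining are assumptions; the conclusion that the gain is unproven does not depend on any single one of them.
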